	8.4.1 Relationship to Study Intervention	15
	8.4.2 Expectedness of SAEs.....	16
	8.4.3 Severity of Event	16
9	STATISTICAL CONSIDERATIONS	126
	9.1 Study Hypotheses	16
	9.2 Sample Size	16
10	SOURCE DOCUMENTS AND ACCESS TO SOURCE DATA/DOCUMENTS	17
11	ETHICS/PROTECTION OF HUMAN SUBJECTS.....	17
	11.1 Ethical Standard	17
	11.2 Institutional Review Board.....	17
	11.3 Informed Consent Process	17
	11.4 Subject Confidentiality	18
12	DATA HANDLING AND RECORD KEEPING.....	18
	12.1 Data Management Responsibilities	18
	12.2 Data Capture Methods	18
	12.3 Types of Data.....	18
	12.4 Protocol Deviations.....	18
13	LITERATURE REFERENCES.....	18
	APPENDICES	20
	APPENDIX A: DYSPORT (ABOBOTULINUMTOXINA) DOSING AND DILUTION GUIDE	201
	APPENDIX B: SCHEDULE OF EVENTS	22

[figure not shown]
LIST OF ABBREVIATIONS

AE	Adverse Event/Adverse Experience
CRF	Case Report Form
eCRF	Electronic Case Report Form
FDA	Food and Drug Administration
GCP	Good Clinical Practice
HIPAA	Health Insurance Portability and Accountability Act
ICF	Informed Consent Form
IRB	Institutional Review Board
MAS	Modified Ashworth Scale
MV	Maximal Velocity
N	Number (typically refers to subjects)
PROM	Passive Range of Motion (ankle)
PI	Principal Investigator
SAE	Serious Adverse Event/Serious Adverse Experience
SOP	Standard Operating Procedure
SSV	Self-Selected Velocity
TS	Tardieu Scale

PROTOCOL SUMMARY

Title:	Video and Temporal Spatial Parameters Assessment of Gait after Dysport treatment: A Pilot Study
Summary:	This pilot study will aim to understand the potential benefit of the assessment of walking using video slow motion for muscle selection and the development of an image catalogue guide of the potential results of injection of abobotulinumtoxinA by comparing foot postures before and after injection.
Objectives:	To evaluate the use of video assessment to improve muscle selection for the injection of botulinum toxin A to improve walking outcomes Primary: SSV, MV, symmetry of walking Secondary: PROM, MAS and TS
Population:	15 persons post stroke or TBI over age 18 with equinovarus foot deformity who are able to ambulate.
Description of Intervention:	Dysport 1000 to 1500 units to be distributed on the basis of clinical indication to ankle plantar flexors (gastrocnemius and soleus), knee extensors and flexors, tibialis posterior and long toe flexors
Study Duration:	Study set-up including IRB/EC approval: 9 months Final study report estimated by: March 2019
Subject Participation Duration:	4-6 weeks

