1 BACKGROUND INFORMATION

Post-stroke, ~40% of patients develop spasticity, with severe or disabling spasticity in up to 15% of patients.^{1,2} Of those who have sustained a traumatic brain injury, approximately 75% develop spasticity, with nearly 50% warranting anti-spasticity treatment.³ Spasticity is a chronic condition defined as “disordered sensory-motor control, resulting from an upper motor neuron lesion, presenting as intermittent or sustained involuntary activation of muscles” with postural limb changes.⁴ Spasticity is characterized by muscle stiffness, paresis, muscle spasms, muscle fatigue, and in some cases rheological change with abnormal lower limb postures.⁵ Beyond the underlying primary disorder and disease, spasticity negatively influences patient function, quality of life and increases caregiver burden.⁶

Hemiparesis from acquired brain injury can also impair mobility, related to abnormal passive and active antagonist muscle resistance.⁴ In chronic hemiparesis, walking speed stabilizes at a low plateau level, in most cases inadequate to sustain community ambulation.⁷ Intramuscular injection of botulinum toxin type A (BoNT-A), produces muscle relaxation for 12–16 weeks or longer and is an effective treatment for lower limb muscle overactivity in spastic paresis.⁸ While botulinum toxin reduces muscle tone and improves spasticity-related features in lower-limb muscles, muscle selection that results in improved walking outcomes have not been explored.⁸

Currently clinical evaluation of the patient with lower limb spasticity after TBI or stroke focuses primarily on physical examination, and in some instances visual assessment of walking. These data, supplemented by registries, illustrations depicting typical patterns, and the potential muscles involved are used to determine the selection of the potential muscles for the injection of botulinum toxin.

This pilot study will aim to understand the potential benefit of the assessment of walking using video slow motion for the muscle selection and develop an image catalogue of the potential results of injection of abobotulinumtoxinA by comparing foot postures before and after injection.

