2 OBJECTIVES

2.1 Study Objectives

Primary objectives: This is a prospective, single arm, non-randomized clinical study designed to evaluate pre-post walking velocity and symmetry with the use of Dysport in patients with equinovarus foot deformity.

Secondary objectives: The study will also **assess** impact of Dysport related to the following measures: ankle and knee PROM, MAS and TS.

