2.2.2 Secondary

Secondary endpoint: ankle and knee PROM, MAS and TS as well as video observational analysis at baseline and follow-up Visits.

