3 STUDY DESIGN

This is a prospective, single arm, non-randomized clinical study with pre-post assessment to include post-stroke and TBI outpatients with spastic ankle / foot muscles amenable to botulinum toxin injection. Subjects must be able to walk without braces.

abobotulinumtoxinA injection in a dose range of 1000 to 1500 units one time to be distributed on the basis of clinical indication to ankle plantar flexors (gastrocnemius and soleus), knee extensors, knee flexors, tibialis posterior and long toe flexors. Administration of the Dysport will be performed by the PI.

First patient expected to be enrolled will be May 2018 and last patient expected to be enrolled will be December 2018. Subjects will be enrolled for a duration of 4-6 weeks.

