4.3 Strategies for Recruitment and Retention

Subjects will be recruited from clinician referrals in the stroke and TBI outpatient clinics, the gait laboratory and patient charts. Subjects will receive the toxin free of charge.

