9.2 Sample Size

For this pilot study, no prospective calculations of statistical power have been made. The sample size of 15 subjects has been selected to provide information on safety, reliability and feasibility of video assisted muscle selection for Dysport injection.

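### The stated aim is to evaluate video-assisted muscle selection, but section 2.1 sets only pre-post Dysport objectives and the protocol text plans no record of muscle choice before and after video

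*Combined protocol and SAP*

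**What the plan says.** Three places present the study as an evaluation of video for choosing muscles.

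- The Protocol Summary objective is "To evaluate the use of video assessment to improve muscle selection for the injection of botulinum toxin A to improve walking outcomes". It attaches SSV, MV and symmetry as primary measures and PROM, MAS and TS as secondary. The summary also names an image catalogue as a product of the study.
- Section 1 aims to "understand the potential benefit of the assessment of walking using video slow motion for the muscle selection", again with the image catalogue.
- Section 9.2 makes no power calculation and says 15 subjects will inform the "safety, reliability and feasibility of video assisted muscle selection for Dysport injection".

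Section 2.1 describes a different study. Its primary objective is "designed to evaluate pre-post walking velocity and symmetry with the use of Dysport in patients with equinovarus foot deformity", and its secondary objective is the impact of Dysport on PROM, MAS and TS. It mentions neither video nor muscle selection.

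Video appears among the endpoints only in section 2.2.2, "as well as video observational analysis at baseline and follow-up Visits". Section 3 has the injection "distributed on the basis of clinical indication to ankle plantar flexors (gastrocnemius and soleus), knee extensors, knee flexors, tibialis posterior and long toe flexors", without mentioning video. Section 5.5 says only that the PI injects the targeted muscle.

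**The concern.** The muscle-selection aim and the section 2.1 objectives are different questions, and the protocol does not say which governs. The planned data serve only the second. A given mean change in velocity or symmetry could arise whether video altered every subject's muscle plan or none, because the plan the PI would have followed without video is not a planned data item. A larger sample would not help, since what is missing is a variable.

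At stake is what the report can conclude. If the protocol is followed exactly, the muscle-selection aim has no planned result, and section 9.2 rests the sample size partly on reliability and feasibility without naming a measure of either. A reader of the final report could take improved walking after injection as support for video-assisted selection, which the design cannot give.

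**Working it through.** **No stated calculation to reproduce.** Section 9.2 gives 15 subjects with no alpha, power, effect size or SD. The check is therefore a comparison of sections.

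**Where muscle choice could be captured**

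| Place | What it contains | Muscle choice before and after video? |
|---|---|---|
| 2.1 | Pre-post objectives with Dysport | No |
| 2.2.1 | Walking velocity and symmetry at two visits | No |
| 2.2.2 | PROM, MAS, TS, video observational analysis at two visits | No |
| 3 and 5.5 | Clinical indication; the targeted muscle | No, and video is not mentioned |
| 6.1 | Video listed among screening measurements | No |
| 6.2 | Video listed ahead of injection | No; no step says it is used to choose muscles |
| 6.3 | Video repeated at follow-up | No |
| 7.1 | SSV, MV, MAS, TS, PROM | No, and no video procedure is described |
| 9.1 | Descriptive summaries of SSV, MV, PROM, TS, MAS | No |
| 12.3 | PROM, MAS, TS, Gait Mat data | No |
| Appendix B | Rows for the same measures and temporal spatial data | No |

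**Why the planned outcomes cannot fill the gap.** For each subject the plan yields a baseline value, a follow-up value and their difference after injection of the muscles finally chosen. The contribution of video to selection is the difference between the final choice and the choice that would have been made without video. Neither choice is a listed data item, and no group is treated without video. The walking and tone changes therefore carry no information on it.

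**Section 9.2, term by term.** Safety is informed by adverse event collection (sections 6 and 8). For reliability no measure is named; the three trials in section 7.1 concern walking speed. For feasibility no measure is named, although section 9.1 puts all collected data into tables and listings, so completed videos could be counted.

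**What a before-and-after record would give at n = 15.** The counts are assumptions, since the documents give none. The exact (Clopper-Pearson) 95% limits for x of n are

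- lower = 0.025 quantile of Beta(x, n − x + 1), taken as 0 when x = 0
- upper = 0.975 quantile of Beta(x + 1, n − x)

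| Selection differed | 95% CI | Width (points) |
|---|---|---|
| 0/15 | 0 to 21.8% | 21.8 |
| 1/15 | 0.2 to 31.9% | 31.7 |
| 3/15 | 4.3 to 48.1% | 43.8 |
| 7/15 | 21.3 to 73.4% | 52.1 |

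Hand check for 0/15: upper = 1 − 0.025^(1/15) = 0.218.

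**The case against.** **It is a small descriptive pilot, so reconciling the objective is enough.** This largely stands. Agreement between the sections is the necessary correction, and an added endpoint is needed only if the sponsor wants to keep the muscle-selection aim. But a descriptive pilot still needs a variable for its stated aim, so leaving the text as it is will not do.

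**The record may exist elsewhere.** The eCRF and the Manual of Procedures named in section 12.4 were not seen. Nor were two removed parts near the front of the document or the body of Appendix A, whose title concerns dosing and dilution. A reader might infer that no such record exists anywhere; the documents support only that the available protocol text does not specify one. A form outside the protocol would still leave the aim without a planned analysis and section 2.1 unreconciled.

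**Usual evaluation already includes watching gait.** Section 1 says current practice includes "in some instances visual assessment of walking". So an evaluation before video may or may not include live gait observation, and the contrast would vary by subject. This stands as a limit on any before-and-after comparison.

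**A before-and-after record would show that video changes plans.** A reader might infer this from the chance of seeing at least one change in 15, which is 1 − 0.8^15 = 96.5% if the true rate were 20% (an assumption). The inference fails. The same unblinded PI chooses twice, so a difference may reflect reconsideration rather than video, and one change in 15 is compatible with rates from 0.2 to 31.9%. The record describes how often the recorded selection differed after viewing. It does not show that selection or walking improved.

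**Feasibility cannot be reported at all.** This would be too strong, because video completion could be counted from the listings. The gap is that no feasibility measure is named.

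**Conclusion.** The point holds for the protocol text available. The Protocol Summary, section 1 and section 9.2 claim an evaluation of video-assisted muscle selection; section 2.1 does not; and nothing in the endpoints, visits, procedures, analysis, data list or schedule captures muscle choice before and after video. Followed exactly, the plan cannot answer its headline aim.

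The gap has no numerical size in the documents: the planned data give no estimate of how often selection differs after video. The intervals shown describe a possible remedy under assumed counts.

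The point is limited. A reader might infer that the pre-post results are undermined or that 15 subjects is the wrong number. Neither follows: the pre-post description, image catalogue and safety data are unaffected, and the fault lies in the aim and the data capture. It should be fixed.

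**What to change.** Required: make the Protocol Summary, section 1 and section 9.2 agree with section 2.1 by choosing one option.

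**Option A, keep the aim.**

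1. After consent and before any study video is viewed (at screening if video is taken then), the PI records by name the muscles intended from the usual clinical evaluation. The PI also notes whether live gait observation, earlier recordings or earlier injection plans were known. After viewing, the same PI records the final selection. This is a record only and does not alter what is injected.
2. Add the record to 6.1, 6.2, 7.1, 12.3 and Appendix B, with a short description of the video viewing step in 7.1.
3. Add one descriptive endpoint to 2.1, 2.2 and 9.1: the proportion of subjects whose recorded selection differed after viewing (at least one muscle added or removed), among those with both records, with an exact 95% CI. List the prior-knowledge notes by subject.
4. State that this describes how often the recorded selection differed. It does not isolate video from reconsideration by the same unblinded PI, and it does not show that selection or walking improved.
5. In 9.2, name a feasibility measure, for example the number of the 15 with usable video viewed before injection and both records complete. Delete the word reliability or name its measure.

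**Option B, text only.** Restate the objective in the Protocol Summary, section 1 and section 9.2 as pre-post change after Dysport plus the image catalogue. Drop the claim to evaluate video-assisted selection, and make no statement that the study shows whether video changes selection.

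**Cost.** Option A needs one eCRF page at existing visits and an IRB-approved amendment (section 11.2), with no extra subjects, visits or staff. Its downsides are a wide interval, a PI who may anchor on the first choice or favour change, and a before-video evaluation that may or may not include live gait observation. Prior knowledge is also likely in some subjects: section 4.1 admits non-naive subjects, and section 4.3 states "Subjects will be recruited from clinician referrals in the stroke and TBI outpatient clinics, the gait laboratory and patient charts". The record is best in place before first enrolment; a later amendment would capture only later subjects. Option B is a text edit, also submitted to the IRB as an amendment.

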1 BACKGROUND INFORMATION

Post-stroke, ~40% of patients develop spasticity, with severe or disabling spasticity in up to 15% of patients.^{1,2} Of those who have sustained a traumatic brain injury, approximately 75% develop spasticity, with nearly 50% warranting anti-spasticity treatment.³ Spasticity is a chronic condition defined as “disordered sensory-motor control, resulting from an upper motor neuron lesion, presenting as intermittent or sustained involuntary activation of muscles” with postural limb changes.⁴ Spasticity is characterized by muscle stiffness, paresis, muscle spasms, muscle fatigue, and in some cases rheological change with abnormal lower limb postures.⁵ Beyond the underlying primary disorder and disease, spasticity negatively influences patient function, quality of life and increases caregiver burden.⁶

Hemiparesis from acquired brain injury can also impair mobility, related to abnormal passive and active antagonist muscle resistance.⁴ In chronic hemiparesis, walking speed stabilizes at a low plateau level, in most cases inadequate to sustain community ambulation.⁷ Intramuscular injection of botulinum toxin type A (BoNT-A), produces muscle relaxation for 12–16 weeks or longer and is an effective treatment for lower limb muscle overactivity in spastic paresis.⁸ While botulinum toxin reduces muscle tone and improves spasticity-related features in lower-limb muscles, muscle selection that results in improved walking outcomes have not been explored.⁸

Currently clinical evaluation of the patient with lower limb spasticity after TBI or stroke focuses primarily on physical examination, and in some instances visual assessment of walking. These data, supplemented by registries, illustrations depicting typical patterns, and the potential muscles involved are used to determine the selection of the potential muscles for the injection of botulinum toxin.

This pilot study will aim to understand the potential benefit of the assessment of walking using video slow motion for the muscle selection and develop an image catalogue of the potential results of injection of abobotulinumtoxinA by comparing foot postures before and after injection.

1.1 Rationale

Current FDA approved dosing for leg muscle injection with abobotulinumtoxina ranges from 1000 to 1500 units to be distributed based on clinical indication to ankle plantar flexors (gastrocnemius and soleus), tibialis posterior and long toe flexors at intervals greater than 3 months. The treatment algorithm may be improved by a dynamic walking visual guidance. We believe visual assessment will improve guidance to muscle selection for treatment, which may result in improvement in foot posture and walking.

1.2 Potential Risks and Benefits

1.2.1 Potential Risks

Lower limb spasticity injection most frequently reported adverse reactions (>2%) are: nasopharyngitis, muscular weakness, musculoskeletal pain, dizziness and falls.

1.2.2 Potential Benefits

Potential benefits of visual assessment during walking may improve functional outcomes. While it may not provide direct benefit to subjects, the importance of the knowledge that may result from the study such as improvement in muscle selection for treatment, patient outcomes and patient satisfaction.

2 OBJECTIVES

2.1 Study Objectives

Primary objectives: This is a prospective, single arm, non-randomized clinical study designed to evaluate pre-post walking velocity and symmetry with the use of Dysport in patients with equinovarus foot deformity.

Secondary objectives: The study will also **assess** impact of Dysport related to the following measures: ankle and knee PROM, MAS and TS.

2.2 Study Outcome Measures

Walking velocity will be collected at baseline and at the follow-up visit using the Gait Mat evaluation. Ankle and knee PROM, MAS and TS data will be collected at baseline and at the follow-up visit.

2.2.1 Primary

Primary endpoint: comparative walking velocity and symmetry of walking at baseline and follow-up visits.

2.2.2 Secondary

Secondary endpoint: ankle and knee PROM, MAS and TS as well as video observational analysis at baseline and follow-up Visits.

3 STUDY DESIGN

This is a prospective, single arm, non-randomized clinical study with pre-post assessment to include post-stroke and TBI outpatients with spastic ankle / foot muscles amenable to botulinum toxin injection. Subjects must be able to walk without braces.

abobotulinumtoxinA injection in a dose range of 1000 to 1500 units one time to be distributed on the basis of clinical indication to ankle plantar flexors (gastrocnemius and soleus), knee extensors, knee flexors, tibialis posterior and long toe flexors. Administration of the Dysport will be performed by the PI.

First patient expected to be enrolled will be May 2018 and last patient expected to be enrolled will be December 2018. Subjects will be enrolled for a duration of 4-6 weeks.

4 STUDY ENROLLMENT AND WITHDRAWAL

4.1 Subject Inclusion Criteria

In order to be eligible to participate in this study, an individual must meet all of the following criteria:

- Provide signed and dated informed consent form
- Willing to comply with all study procedures and be available for the duration of the study
- Male or female, aged ≥ 18
- Equinovarus foot deformity appropriate for botulinum toxin treatment (naïve or non-naïve)
- MAS between 1 to 3
- Women of reproductive potential must use effective contraception for the duration of the study
- Able to walk a few steps without a brace for the purpose of the video observation

4.2 Subject Exclusion Criteria

An individual who meets any of the following criteria will be excluded from participation in this study:

- Previous surgical intervention to affected/ankle/foot
- Uncontrolled seizures
- Pregnancy or lactation
- Known allergic reactions to Dysport
- Treatment with another investigational drug or other intervention in the past 4 months
- MAS 4
- Anything that would place the individual at increased risk or preclude the individual's full compliance with or completion of the study
- Lower motor neuron disorder
- < Four months post botulinum toxin or serial casting

4.3 Strategies for Recruitment and Retention

Subjects will be recruited from clinician referrals in the stroke and TBI outpatient clinics, the gait laboratory and patient charts. Subjects will receive the toxin free of charge.

4.4 Subject Withdrawal

Subjects may withdraw voluntarily from the study or the investigator may terminate a subject's participation.

4.4.1 Reasons for Withdrawal

Subjects are free to withdraw from participation in the study at any time upon request.

An investigator may terminate a study subject's participation in the study if:

- Any clinical adverse event (AE) or other medical condition or situation occurs such that continued participation in the study would not be in the best interest of the subject.
- The subject meets an exclusion criterion (either newly developed or not previously recognized) that precludes further study participation.

